## 11 ADVERSE EXPERIENCE REPORTING AND DOCUMENTATION

### 11.1 Adverse Events

An adverse event (AE) is any untoward medical occurrence in a clinical investigation of a patient-administered pharmaceutical product and that does not necessarily have a causal relationship with the treatment. An AE is therefore any unfavorable and unintended sign (including an abnormal laboratory finding), symptom or disease temporally associated with the administration of an investigational product, whether or not related to that investigational product. An unexpected AE is one of a type not identified in nature, severity, or frequency in the current Investigator's Brochure or of greater severity or frequency than expected based on the information in the Investigator's Brochure.

The Investigator or research assistant will probe, via discussion with the subject, for the occurrence of AEs during each subject visit and record the information in the site's source documents. Adverse events will be recorded in the patient CRF. Adverse events will be described by duration (start and stop dates and times), severity, outcome, treatment and relation to study drug, or if unrelated, the cause.

#### 11.1.1 AE Severity

The National Cancer Institute's Common Terminology Criteria for Adverse Events (CTCAE) Version 3.0 should be used to assess and grade AE severity, including laboratory abnormalities judged to be clinically significant. The modified criteria can be found in the study manual. If the experience is not covered in the modified criteria, the guidelines shown in Table 1 below should be used to grade severity. It should be pointed out that the term "severe" is a measure of intensity and that a severe AE is not necessarily serious.

**Table 1. AE Severity Grading**

Severity (Toxicity Grade)	Description
Mild (1)	Transient or mild discomfort; no limitation in activity; no medical intervention or therapy required. The subject may be aware of the sign or symptom but tolerates it reasonably well.
Moderate (2)	Mild to moderate limitation in activity, no or minimal medical intervention/therapy required.
Severe (3)	Marked limitation in activity, medical intervention/therapy required, hospitalizations possible.
Life-threatening (4)	The subject is at risk of death due to the adverse experience as it occurred. This does not refer to an experience that hypothetically might have caused death if it were more severe.

#### 11.1.2 AE Relationship to Study Drug

The relationship of an AE to the study drug should be assessed using the following the guidelines in Table 2.

**Table 2. AE Relationship to Study Drug**

Relationship to Drug	Comment
Definitely	Previously known toxicity of agent; or an event that follows a reasonable temporal sequence from administration of the drug; that follows a known or expected response pattern to the suspected drug; that is confirmed by stopping or reducing the dosage of the drug; and that is not explained by any other reasonable hypothesis.
Probably	An event that follows a reasonable temporal sequence from administration of the drug; that follows a known or expected response pattern to the suspected drug; that is confirmed by stopping or reducing the dosage of the drug; and that is unlikely to be explained by the known characteristics of the subject's clinical state or by other interventions.
Possibly	An event that follows a reasonable temporal sequence from administration of the drug; that follows a known or expected response pattern to that suspected drug; but that could readily have been produced by a number of other factors.
Unrelated	An event that can be determined with certainty to have no relationship to the study drug.

## 11.2 Serious Adverse Experiences (SAE)

An SAE is defined as any AE occurring at any dose that results in any of the following outcomes:

- Death
- a life-threatening adverse experience
- inpatient hospitalization or prolongation of existing hospitalization
- a persistent or significant disability/incapacity
- a congenital anomaly/birth defect

Other important medical events may also be considered an SAE when, based on appropriate medical judgment, they jeopardize the subject or require intervention to prevent one of the outcomes listed.

### 11.2.1 Serious Adverse Experience Reporting

Study sites will document all SAEs that occur (whether or not related to study drug) per [UCSF HRPP Guidelines](#). The collection period for all SAEs will begin after informed consent is obtained and end after procedures for the final study visit have been completed.

In accordance with the standard operating procedures and policies of the local Institutional Review Board (IRB)/Independent Ethics Committee (IEC), the site investigator will report SAEs to the IRB/IEC.

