pressure medication and diuretic, and also commonly used for treating symptoms of high androgens including acne and hirsutism at a starting dose of 100mg daily. This medication has a longstanding history of favorable side effects profiles. The most likely side effect is increased urination. Other side effects with a dose of 100mg daily in the absence of renal failure (an exclusion criterion for the current study) are < 1%.

Potential side effects include breast tenderness, tiredness, headache, dizziness, lightheadedness, diarrhea, cramping, nausea, vomiting, fever, or confusion. There is a low risk of renal insufficiency, electrolyte disturbances, dizziness and/or dehydration. To minimize any harm, all participants will have baseline renal and electrolytes obtained, an in-person study visit within one month of treatment initiation and then every 3 months thereafter to obtain subjective information regarding medication tolerability, to obtain vital signs, as well as laboratory assessment of sodium, potassium, and creatinine levels. All values will be reviewed by the principal investigator and Data Safety Monitoring Board to determine whether the current dose may be maintained, decreased, or discontinued.

Spironolactone is categorized as Pregnancy Class C due to potential risk of feminization seen in animal studies of male fetuses, though no studies have implicated spironolactone in these birth defects in humans. Urine pregnancy testing will be performed every 4 weeks in all pre-menopausal women. Urine pregnancy testing is not required for women who are not sexually active with men. As sex organ development begins between 6-8 weeks of gestational age, spironolactone would be discontinued no later than week 4 of conception to avoid fetal risk if a woman were to become pregnant.

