### **4 STUDY DESIGN**

#### **4.1 Study Overview**

This is a single center, double-blind, placebo-controlled, randomized (2:1), parallel group pilot clinical trial. 30 women are targeted for enrollment. Each participant will be administered a single dose of spironolactone or placebo once daily for a total of 6 months. In person evaluations will take place at Month 1, 3, 6, and at the follow up visit within 3 months of end of treatment (up to Month 9). Participants may opt to extend the

study treatment period to 12 months. Participants who opt to extend will complete additional in person evaluations at Month 9 and Month 12. Screening data will be reviewed to determine subject eligibility. Subjects who meet all inclusion criteria and none of the exclusion criteria will be entered into the study.

The following treatment regimens will be used:

- Experimental treatment – spironolactone, 100 mg once daily
- Placebo or Comparator – one capsule, once daily

Total duration of study treatment will be 6 months or 12 months. Total duration of the study is expected to be  $\leq 10$  or  $\leq 16$  months (including up to 1 month for screening).

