### **5.3 Safety Evaluations**

- In-person visits will be conducted at baseline, at one month (given highest risk of adverse events in first month of drug exposure) and every 3 months thereafter. Additionally women will be seen within 3 months after end of treatment to ensure resolution of any drug related side effects. In-person study visits will include a physical exam with vital signs, anthropomorphic measurements, assessment of adherence with pill counts, assessment of side effects, and performance of safety monitoring labs including electrolytes, renal function and urine pregnancy tests. Each visit will also include contraceptive counseling for pre-menopausal women because spironolactone has potential risk of feminization seen in animal studies of male fetuses, though no studies have implicated spironolactone in these birth defects in humans. Pregnancy testing will be performed every month to ensure that if a participant were to become pregnant, spironolactone is discontinued within 4 weeks of conception. This will ensure no fetal risks as human sex organ development begins between 6-8 gestational weeks.
- There will be continuous safety surveillance of participants through the reporting of incidence of adverse events (AEs). AEs will be recorded in a systematic manner at every study visit and when otherwise volunteered by the participant.

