### **12 DISCONTINUATION AND REPLACEMENT OF SUBJECTS**

#### **12.1 Early Discontinuation of Study Drug**

A subject may be discontinued from study treatment at any time if the subject, the investigator, or the Sponsor feels that it is not in the subject's best interest to continue. The following is a list of possible reasons for study treatment discontinuation:

- Subject withdrawal of consent (or assent)
- Subject is not compliant with study procedures
- Protocol violation requiring discontinuation of study treatment
- Adverse event that in the opinion of the investigator would be in the best interest of the subject to discontinue study treatment
- Lost to follow-up
- Positive pregnancy test

If a subject is withdrawn from treatment due to an adverse event, the subject will be followed and treated by the Investigator until the abnormal parameter or symptom has resolved or stabilized.

All subjects who discontinue study treatment should come in for End of Treatment visit as soon as possible and be encouraged to complete all visit procedures.

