## APPENDIX 1. Schedule of Events

	Screening	Baseline/ Day 1	Month 1	Month 3	Month 6 End of Study/ Treatment	Month 9*	Month 12* End of Study/ Treatment	Follow-Up within 3 months of EOS/EOT
	Visit 1	Visit 2	Visit 3	Visit 4	Visit 5	Visit 6	Visit 7	
Obtain informed consent	X							
Review your medical history	X							
Review medications you are taking	X	X	X	X	X	X	X	X
Perform complete physical exam	X							
Perform physical exam depending on your symptoms			X	X	X	X	X	
Measure your vital signs (blood pressure, heart rate)	X		X	X	X	X	X	
Measure your weight and height	X a		X	X	X	X	X	
Measure your waist circumference	X				X		X	
Review your general health (side effects and illnesses)		X	X	X	X	X	X	X
Draw samples of your blood for to check your general health, liver health, cholesterol, glucose, and insulin levels	X		X	X	X	X	X	
Draw samples of your blood to check your sex hormone levels	X				X		X	
If you are a female who can have children, collect a sample of your urine for pregnancy	X b		X	X	X	X	X	
Collect a small liver sample (biopsy)	X c				X*		X*	
Scan your liver: MRI-PDFF and MRE		X			X		X	
Give you study drug and instructions on how to take it		X	X	X	X	X	X	
Review the amount of study drug you have taken and collect unused			X	X	X	X	X	

a Height only measured at Screening

b In addition, home pregnancy tests are to be performed by women who can have children every 4 weeks from Day 1 until End of Study/Treatment

c Performed prior to screening as part of your standard of care for NASH

\*Optional visits/procedures

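### SAE collection closes at the final study visit with no visible provision to follow a pregnancy to its outcome, so a birth defect after on-study conception would generally fall outside the window

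*Combined protocol and SAP*

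**What the plan says.** Section 11.2 lists "a congenital anomaly/birth defect" among the outcomes that make an adverse event serious. Section 5.3 states that "spironolactone has potential risk of feminization seen in animal studies of male fetuses", and section 2.1 gives the same warning. Both add that no human study has implicated the drug in such defects.

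Section 11.2.1 sets one collection period for every SAE: "The collection period for all SAEs will begin after informed consent is obtained and end after procedures for the final study visit have been completed". It documents SAEs under institutional guidelines but makes no exception of its own for pregnancy.

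The steps after a positive test are spread over several sections:

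- Section 9.2.2: study drug is stopped at once and the site is told.
- Section 8.2: pregnancy is the one condition certain to lead to unblinding.
- Section 12.1: a positive pregnancy test is a listed reason for stopping treatment, and "All subjects who discontinue study treatment should come in for End of Treatment visit as soon as possible".
- Appendix 1: the last column is "Follow-Up within 3 months of EOS/EOT". Section 10.5 limits that contact to adverse experiences and medication changes.

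Section 12.1 also follows a woman until a problem resolves or settles, but only when an adverse event caused her withdrawal from treatment. A positive pregnancy test is a separate entry in that list.

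**The concern.** The protocol defines an SAE that is mostly recognised at birth, names a drug risk of that kind, and then ends SAE collection at a visit that its own steps bring forward once pregnancy is found. Testing frequency does not bear on this. Even with every pregnancy found promptly, nothing in the text available has anyone ask how it ended or how the newborn was.

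At stake is one piece of safety information, not an efficacy or feasibility result. Section 5.3 reasons that stopping the drug within 4 weeks of conception removes the fetal risk, but no outcome would be collected against which to check that reasoning. A safety table with no congenital anomalies would tell a reader little, because the collection period would usually have ended before one could be seen. Enrolment is limited to women aged 18 to 45, with perimenopausal women excluded, so pregnancy is a foreseeable event.

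**Working it through.** **Inputs from the protocol.** Screening up to 1 month, treatment 6 or 12 months, follow-up up to 3 months after treatment (Synopsis, section 4.1). Drug stopped within 4 weeks, or 28 days, of conception (section 5.3). 30 women, 20 on spironolactone and 10 on placebo (Synopsis).

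**Assumptions not in the protocol.** Conception to birth 266 days, range 238 to 280. Pregnancy rate 1 to 8% per woman-year.

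**The plan's own durations.** 1 + 6 + 3 = 10 months and 1 + 12 + 3 = 16 months, as the Synopsis states.

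**Route A: the steps set for a positive test.** The window closes at the day drug is stopped plus at most 3 months (3 × 365.25/12 ≈ 91 days). The gap is conception-to-birth time minus that day. Later detection is included as a sensitivity check.

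| Drug stopped, days after conception | Window closes, days after conception | Gap if birth at 238 days | at 266 days | at 280 days |
|---|---|---|---|---|
| 28 | 28 + 91 = 119 | 119 | 147 | 161 |
| 56 | 56 + 91 = 147 | 91 | 119 | 133 |
| 84 | 84 + 91 = 175 | 63 | 91 | 105 |

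At the protocol's 28 days, the window closes at 119/7 = 17 weeks. The gap is 119/7 = 17 weeks to 161/7 = 23 weeks, and 147/7 = 21 weeks at the central assumption. No combination in the table closes it; the smallest gap is 63 days.

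**Route B: the woman stays on the planned visit schedule.** The final visit is then at Month 9 (day 274), or at Month 15 (day 457) if she extends. The latest conception that would be born by then is the final-visit day minus conception-to-birth time.

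- 6-month schedule: 274 − 266 = day 8, about 4% of roughly 183 treatment days (range 0 to 20%).
- 12-month schedule: 457 − 266 = day 191, about 52% of roughly 365 treatment days (range 48 to 60%).
- Conception at the last dose, either schedule: 266 − 91 = 175 days short (range 238 − 91 = 147 to 280 − 91 = 189).

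**Expected number of pregnancies during treatment.**

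- Both arms: 30 × 0.5 to 30 × 1 = 15 to 30 woman-years. 15 × 0.01 = 0.15; 30 × 0.08 = 2.4.
- Spironolactone only: 20 × 0.5 to 20 × 1 = 10 to 20 woman-years. 10 × 0.01 = 0.1; 20 × 0.08 = 1.6.

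**The case against.** The strongest reply has four parts.

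**The window does not shut out every case.** An anomaly found before birth, or at a pregnancy loss, before the final visit is inside it. The Synopsis also promises to seek complete follow-up on every randomized woman whatever her adherence. If that keeps a pregnant woman on the planned schedule, Route B applies and some early conceptions would be born in time. This stands as a limit on the claim. It is the weaker reading for live births, because section 12.1 brings the End of Treatment visit forward and section 11.3 keeps only temporarily discontinued women on the regular schedule. On the 6-month schedule it rescues very little.

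**Other duties could bring a case to light.** Section 17.5, item 8, requires prompt reporting of unanticipated problems involving risk to subjects or others. Section 17.2 requires the IRB to be told of new information bearing on patient safety. Neither is tied to the SAE period, so a defect that became known might well be reported. Neither makes anyone look for it.

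**Some text could not be seen.** The institutional guidelines cited in section 11.2.1, the consent form and the text of section 11.4 (Medical Monitoring) were not available. A pregnancy-reporting rule could sit in any of them. Section 11.2.1 would still need to agree with it, since it fixes the period for all SAEs.

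**The risk is small and already managed.** The protocol has monthly testing, contraceptive counselling, an exclusion for women unwilling to use birth control, a stated timing rationale and unblinding on pregnancy. Ten of the 30 women take placebo. No feasibility endpoint or analysis in section 15 depends on pregnancy outcomes, and a trial of this size could not estimate an anomaly rate even with full follow-up. This bears on how serious the point is and stands in full.

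**Conclusion.** The point holds in limited form. On the route the protocol sets after a positive test, SAE collection ends at most about 17 weeks after conception, roughly 17 to 23 weeks before birth. A birth defect would generally fall outside the period and would not be actively sought. The size rests on the assumed 238 to 280 days from conception to birth and on the protocol's 4-week figure; later detection narrows the gap without closing it.

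A reader might infer that no congenital anomaly could ever be captured, or that one would never reach the IRB. The documents do not support either: prenatal findings, losses and some early conceptions can fall inside the window, and general reporting duties continue outside it. Nor do they support the inference that a planned analysis is invalid or that the trial sets out to claim an absence of birth defects.

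This is a cheap safety improvement that should be made, not a flaw that undermines the trial. With an assumed 0.15 to 2.4 pregnancies during treatment across both arms, it may never be called on.

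**What to change.** Reconcile sections 11.2, 11.2.1 and 12.1 with one exception to the collection period. Suggested text for section 11.2.1: for any pregnancy conceived between first dose and the follow-up visit, in either arm, SAE collection remains open until the pregnancy outcome and the newborn's findings have been obtained by telephone or from medical records and reported to the IRB and DSMB. Add a matching line to section 12.1, and to the consent form if it does not already allow for this. If the institutional guidelines already require it, cite them there and align the closing date.

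The change concerns data collection only and leaves treatment, stopping rules, sample size and planned analyses alone. It costs a protocol sentence, a line in section 12.1, possibly a consent line, and one or two calls or record requests for probably 0 to 2 women. The downside is that a case may still be open after the woman's last visit; it can be reported as an addendum.

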## 11.3 Investigational Product Adjustment & Interruption Criteria

Dosage for investigational product should be held constant throughout the course of the study. In the event that the subject experiences adverse experiences that the Investigator suspects are related to the investigational product, a dosage adjustment or interruption of investigational product may be implemented. Subjects may also be permanently discontinued from investigational product by the Investigator at any time for clinical safety.

concerns (see section 12.3).

Subjects who are temporarily discontinued from investigational product are expected to continue in the study and should follow the regular visit schedule for the duration of the study. Rechallenge with investigational product may be initiated at the Investigator's discretion upon discussion with the medical monitor. Additional safety monitoring may be initiated.

### **12 DISCONTINUATION AND REPLACEMENT OF SUBJECTS**

#### **12.1 Early Discontinuation of Study Drug**

A subject may be discontinued from study treatment at any time if the subject, the investigator, or the Sponsor feels that it is not in the subject's best interest to continue. The following is a list of possible reasons for study treatment discontinuation:

- Subject withdrawal of consent (or assent)
- Subject is not compliant with study procedures
- Protocol violation requiring discontinuation of study treatment
- Adverse event that in the opinion of the investigator would be in the best interest of the subject to discontinue study treatment
- Lost to follow-up
- Positive pregnancy test

If a subject is withdrawn from treatment due to an adverse event, the subject will be followed and treated by the Investigator until the abnormal parameter or symptom has resolved or stabilized.

All subjects who discontinue study treatment should come in for End of Treatment visit as soon as possible and be encouraged to complete all visit procedures.

#### **12.2 Withdrawal of Subjects**

A subject may be withdrawn from the study at any time if the subject, the investigator, or the Sponsor feels that it is not in the subject's best interest to continue.

All subjects are free to withdraw from participation at any time, for any reason, specified or unspecified, and without prejudice.

Reasonable attempts will be made by the investigator to provide a reason for subject withdrawals. The reason for the subject's withdrawal from the study will be specified in the subject's source documents. Refer to Section 10 for End of Treatment procedures.

#### **12.3 Replacement of Subjects**

Subjects who withdraw from the study treatment will be replaced.

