NUMBER OF SUBJECTS	30 total women: 20 randomized to spironolactone and 10 randomized to placebo
SUBJECT SELECTION CRITERIA	
Key Inclusion Criteria:
 
 
- Women with NASH identified on standard of care liver biopsy performed for clinical purposes.
 
 
Key Exclusion Criteria:
 
 
- Uncontrolled diabetes
 
- Alcohol consumption >2 drinks per day for at least 3 consecutive months over the previous 5 years
 
- Other chronic liver disease (i.e. hepatitis B virus, hepatitis C virus, autoimmune hepatitis) or cirrhosis from any cause
 
- Recent or planned upcoming weight reduction surgery within five years of diagnosis of biopsy-confirmed NASH
 
- HIV infection
 
- Drugs associated with fatty liver (i.e. amiodarone, methotrexate, systemic glucocorticoids, tamoxifen, anabolic steroids, valproic acid) for more than 4 weeks prior to baseline or during study
 
- Recent, current, or planned upcoming pregnancy or current perimenopausal status
 
- Renal impairment (glomerular filtration rate <45 ml/min/1.73m or potassium levels > 5.0 mmol/L)
 
- Androgen receptor antagonist use (i.e. flutamide, spironolactone or flutamide) for more than 3 months within one year prior to baseline
 

TEST PRODUCT, DOSE, AND ROUTE OF ADMINISTRATION	Spironolactone 100mg. Product will be administered orally once daily for a length of 6 to 12 months.
CONTROL PRODUCT, DOSE AND ROUTE OF ADMINISTRATION	Placebo. Product will be administered orally once daily for a length of 6 months.
DURATION OF SUBJECT PARTICIPATION AND DURATION OF STUDY	
Subjects will be on study for up to 10 or 16 months
 
Screening: up to one month
 
Treatment: 6 to 12 months
 
Follow-up: up to 3 months from end of treatment
 
The total duration of the study is expected to be 4 years. Women will be enrolled and treated on a rolling basis, with a 30 month total recruitment period, 6 to 12 months of treatment per participant, and up to 3 months for the final subject follow-up post treatment.

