## 8 STUDY TREATMENTS

### 8.1 Method of Assigning Subjects to Treatment Groups

The UCSF pharmacy will generate a randomization table using random number generating software, assigning patients on a 2:1 basis to spironolactone or placebo in a blocked randomization scheme. Patients will be assigned to a treatment arm in the order to which they present for the first day of dosing. Patients assigned to a treatment arm who later drop out of the study will not be replaced in the randomization scheme.

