## **8.4 Supply of Study Drug at the Site**

The UCSF Investigational Drug Service (IDS) will receive the bulk supplies of spironolactone and matching placebo from the compounding pharmacy. Capsules will be stored, accounted for, assigned per the randomization schedule and packaged and labeled for dispensing to the subject by the IDS pharmacy staff once ordered by the investigator on a study order/prescription form.

Drug will be provided by the manufacturer to the UCSF Investigational Pharmacy every three months. Subjects who were randomized and not treated will be immediately replaced when an “earlier” slot becomes available due to the dropped subject.

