### **10.2 Visit 2 (Day 1/Baseline)**

- Record any Adverse Experiences.
- Concomitant medications review.

- Assess liver stiffness by MRE and MRI-PDFF
- Randomize to treatment group, dispense study drug, and provide instructions on how to take it.

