### **15.1 Data Sets Analyzed**

All eligible patients will be included in the feasibility analyses because a key feature of this study is to determine the proportion of eligible patients that agree to participate. Only those randomized participants will be included in the analyses of secondary outcomes, though analyses will be conducted and presented separately as intention to treat, per protocol, and as treated, as the information gleaned from these different analytic approaches provides different, clinically relevant information.

All eligible patients who are randomized into the study and receive at least one dose of the study drug (the Safety Population) will be included in the safety analysis.

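### The protocol conflicts on whether Month 6 MRI and laboratory outcomes are due after permanent stopping of study drug, and its replacement rules (8.1, 8.4, 12.3) need reconciling

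*Combined protocol and SAP*

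**What the plan says.** **Assessments after stopping.** Section 12.1 asks all women who discontinue study treatment to attend an End of Treatment visit promptly and encourages them to complete all its procedures. Section 10.4 and Appendix 1 describe one visit that is both Month 6 and the end of study and treatment. It includes MRE, MRI-PDFF, laboratory tests and the optional biopsy. Section 11.3 says that women who stop temporarily continue on the regular visit schedule. For permanent discontinuation it refers to Section 12.3, which contains one sentence: "Subjects who withdraw from the study treatment will be replaced".

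Sections 4.1 (visits), 9.2.3 (sex hormones) and 9.4 (MRI) list Month 6 without making it depend on still taking study drug. The Primary Analysis Plan in the synopsis commits to intention to treat and to attempting complete follow-up of every randomized woman irrespective of adherence.

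**Replacement.** Section 8.1: "Patients assigned to a treatment arm who later drop out of the study will not be replaced in the randomization scheme". Section 8.4: "Subjects who were randomized and not treated will be immediately replaced", when an earlier "slot becomes available due to the dropped subject". Section 12.3 refers to neither. The planned total is "30 total women: 20 randomized to spironolactone and 10 randomized to placebo".

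**Analysis sets.** Section 15.1 says "All eligible patients will be included in the feasibility analyses" and "Only those randomized participants will be included in the analyses of secondary outcomes". Dropout is a feasibility endpoint in Section 5.1, and Section 15.3 gives completing follow-up an exact confidence interval. Neither section states a denominator.

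**The concern.** The main issue is when outcomes are measured. A coordinator following Section 12.1 could reasonably log the early visit as Visit 5 and not recall the woman at Month 6. Her scan and blood results, taken at whatever time she stopped, could then be analysed alongside true Month 6 values. If stopping is more common or earlier in one arm, the two arms are measured at different average times, and a between-group difference partly reflects that.

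The lesser issue is record-keeping at randomization. If a freed slot is re-used as Section 8.4 describes, two women share one assignment, and the first could be lost from the record of her arm. If Section 12.3 means recruiting further women, the total randomized could exceed the stated 30.

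**Working it through.** **1. The plan's own figure.** 30 × 2/3 = 20 and 30 × 1/3 = 10, so the stated split is consistent. Section 15.6 bases the 30 on budget and feasibility. The documents give no dropout or stopping rate, so every rate below is an assumption.

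**2. Month 6 after permanent stopping, passages side by side.**
- Towards the early visit taking the place of Month 6: Section 12.1 with Section 10.4 and Appendix 1 (one visit, two names), and Section 11.3 (regular schedule stated only for temporary stopping).
- Towards Month 6 still being due: Sections 4.1, 9.2.3 and 9.4, and the synopsis aim.
- No sentence settles it, and the reference that should (11.3 to 12.3) leads only to the replacement sentence.

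**3. If the early visit is taken as Visit 5.** Only Follow-Up remains, within 3 months of end of treatment. For a stop at Month 1, the last visit falls by about 1 + 3 = Month 4.

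Follow-Up would not fill the gap. Section 10.5 and Appendix 1 list only adverse events and medications for it. Section 4.1 makes it an in-person visit, and Sections 5.3 and 9.2.1 attach laboratory tests to in-person visits. That is a further inconsistency. On either reading, Follow-Up provides no Month 6 MRI.

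**4. Size of the timing shift.** Assume a fraction s stops at month t, all of them attend the early visit and have its assessments, and everyone else is measured at exactly Month 6. Then mean time = 6(1 − s) + s·t.

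| s | Women of 30 | t = 1 | t = 3 |
|---|---|---|---|
| 10% | 3 | 5.5 | 5.7 |
| 20% | 6 | 5.0 | 5.4 |
| 30% | 9 | 4.5 | 5.1 |

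By arm, if 4/20 and 1/10 stop at Month 1:
- spironolactone (16 × 6 + 4 × 1)/20 = 5.0 months
- placebo (9 × 6 + 1 × 1)/10 = 5.5 months

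**5. Replacement.** Total randomized if each withdrawal is replaced once is 30 + 30s: 33, 36 or 39 at 10%, 20% or 30%. If replacement continues until 30 complete treatment, it is 30/(1 − s) = 33.3, 37.5 or 42.9, rounded up to 34, 38 or 43.

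Study dropout with every randomized woman counted, if 20% stop and all of them leave (exact 95% CI):
- no replacement: 6/30 = 20% (8–39%)
- replaced once: 7/36 = 19% (8–36%)
- until 30 complete treatment: 8/38 = 21% (10–37%)

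The expected counts are 6.0, 7.2 and 7.6, each 20% before rounding, so the spread in the point estimates is rounding. If only half of those who stop leave, the figures are 3/30 = 10% (2–27%), 4/36 = 11% (3–26%) and 4/38 = 11% (3–25%).

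**The case against.** **An added early visit does not cancel Month 6.** This stands. Stopping drug (12.1) and leaving the study (12.2) are separate sections, and the unconditional schedule and the synopsis aim favour continued follow-up. A reader might infer that the protocol ends assessment of permanent stoppers before Month 6, or uses their early values as Month 6 values. No passage says either. What remains is that procedures and aim are not joined, so the site can act on either reading.

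**Follow-Up may include laboratory tests.** This also stands. It would be too strong to say that Follow-Up settles the matter by recording only events and medications, since Sections 4.1, 5.3 and 9.2.1 point the other way.

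**The replacement conflict is narrow.** Largely right. Section 10.2 has staff "Randomize to treatment group, dispense study drug, and provide instructions on how to take it" at one visit, so few women should be randomized and never treated. Section 8.4 may be meant as an exception to 8.1, and 12.3 may mean an extra woman on a new code. The text says neither.

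**Replacement could hide dropout.** A reader might infer this. With 6 dropouts, all replaced by women who complete, completion would read 30/30 (exact 95% CI 88–100%) if the replaced women were left out. It would be 30/36 = 83% (67–94%) with everyone counted, and 24/30 = 80% (61–92%) with no replacement. But no passage leaves them out, and the synopsis and Section 15.1 point to keeping them in.

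**The timing example is hypothetical.** Agreed. It assumes that all who stop attend the early visit. Those who leave instead contribute missing data, not early data. No outcome shift can be estimated from the documents, and the trial is stated not to be powered for NASH progression.

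**Conclusion.** The point holds as a conflict between passages, with moderate confidence. The protocol does not settle whether Month 6 MRI and laboratory outcomes are due after permanent stopping. If the early visit is used in their place, the arms could be measured about half a month apart on average under the assumed 4/20 and 1/10 stopping at Month 1. Later or more balanced stopping would give a smaller gap. This is a risk to the between-group comparison of secondary outcomes, and the size of any resulting bias is unknown.

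The replacement conflict is secondary. Its practical risks are two women on one assignment and a total above 30. Its effect on the dropout rate is small when every randomized woman is counted. The missing denominators alone would be detail that the promised SAP can supply. No figure in the plan is shown to be wrong.

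**What to change.** 1. **Sections 12.1 and 11.3.** State that women who permanently stop study drug before Month 6 are still asked for the scheduled Month 6 MRI and laboratory outcomes, unless they withdraw consent or the investigator judges an assessment unsuitable. Record early End of Treatment data with their actual date and do not use them as Month 6 values. Correct the reference in 11.3. Reconcile 10.5 and Appendix 1 with 4.1, 5.3 and 9.2.1 on what is done at Follow-Up.
2. **Sections 8.1, 8.4 and 12.3.** Write one rule: a randomized woman stays in her assigned arm, her slot is never re-used, any additional woman takes the next unused code, and the total randomized is reported by arm.
3. **Promised SAP.** Count every randomized woman in the denominators for dropout and for completing follow-up.

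The cost is a short text amendment, and the Month 6 assessments are already in the schedule. The downsides are one more visit and possibly a second scan for a few women, some missing Month 6 values where early ones would otherwise have been used, and possibly a less favourable retention figure.
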